4. TRIAL DESIGN

4.1. Primary and secondary parameters to be determined during the study

Primary variable:

- Change in HFcomponent after 5-minute exposure to the VR audio-visual sequence;

Secondary variables:

- rMSSD variable after 5-minute exposure to the VR audio-visual sequence;

- LF/HF ratio after 5-minute exposure to the VR audio-visual sequence;
- SDNN variable after 5-minute exposure to the VR audio-visual sequence;
- Total power (TP) variable after 5-minute exposure to the VR audio-visual sequence;
- HR variable after 5-minute exposure to the VR audio-visual sequence;
- BP variable after 5-minute exposure to the VR audio-visual sequence;
- Spielberger State-Trait Anxiety Inventory (STAI) variable after 5-minute exposure to the VR audio-visual sequence.

The criterion for the prevailing efficiency for each variable is the presence of statistically significant differences between groups in favour of any of the groups with a directivity, which indicates the effectiveness of the impact of the studied VR technology.

Tolerability evaluation

Tolerability of the VR technology will be evaluated based on: vital signs, assessment of AR/ADE.

Upon completion of the study (upon completion of Visit 2), the Investigator should provide an assessment of the tolerability of the studied VR technology for each healthy volunteer based on the 5-point verbal analogue scale given in Table 1.

Table 1. Tolerability evaluation

Points	Category	Category description
5 points	“very good ”	No adverse reactions associated with the VR technology
4 points	“good”	There is a minor adverse effect that does not cause serious problems in a healthy volunteer and does not require discontinuation of the use of the VR technology.
3 points	“satisfactory”	There is a minor adverse effect that causes discomfort in a healthy volunteer, but does not require discontinuation of the use of the VR technology.
2 points	“unsatisfactory”	There is an adverse reaction that causes a significant negative effect on the condition of a healthy volunteer, it requires discontinuation of the use of the VR technology, but does not require additional medical care
1 point	“extremely unsatisfactory”	There is an adverse reaction that causes a significant negative effect on the condition of a healthy volunteer, it requires discontinuation of the use of the VR technology and additional medical care

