4.2. Description of type/design of the trial/randomization/intended purpose of the VR technology

PurePurr-001 is a randomized, prospective, sham-controlled, blinded, cross-over clinical study. The study will include healthy volunteers aged 20 to 60 years, who have applied to the study site for other medical reasons or those who read the advertisement on the Internet. After signing the Informed Consent Form for participation in the clinical study, an assessment of healthy volunteers’ eligibility with the inclusion/non-inclusion criteria will be carried out.

Study groups

Eligible volunteers will be randomized at the 1:1 ratio to one of the following study groups (1 or 2):

Group 1: the volunteers will first be tested with the VR headset A, and during the next visit – with the VR headset B.

Group 2: the volunteers will first be tested with the VR headset B, and during the next visit – with the VR headset A.

Visits

The study includes two visits:

Visit 1 (Day 1): verification of inclusion/non-inclusion criteria, randomization, and testing.

Visit 2 (Day 2): verification of exclusion criteria, testing.

The minimum interval between the two visits is 24 hours and nocturnal sleep is mandatory. The next visit should take place at the same time, taking into account the circadian rhythms. The overall

duration of the study for each volunteer is 2 days (+7 days), if necessary, Visit 2 may be postponed for a maximum period of 7 days.

Stages of each visit are described in details in Section 6.1.

Layout 1. General study layout

Group 1

Headset A, Visit 1

Stage 1	Stage 2	Stage 3	Stage 4
---------	---------	---------	---------

Headset B, Visit 2

Stage 1	Stage 2	Stage 3	Stage 4
---------	---------	---------	---------

Group 2

Headset B, Visit 1

Stage 1	Stage 2	Stage 3	Stage 4
---------	---------	---------	---------

Headset A, Visit 2

Stage 1	Stage 2	Stage 4	Stage 4
---------	---------	---------	---------

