7. EFFICACY EVALUATION

7.1. Efficacy parameters

Principal and secondary parameters to be determined during the study:

Primary variable:

- Change in HF component after 5-minute exposure to the VR audio-visual sequence;

Secondary variables:

- Change in rMSSD after 5-minute exposure to the VR audio-visual sequence;
- Change in LF/HF ratio after 5-minute exposure to the VR audio-visual sequence;
- Change in SDNN after 5-minute exposure to the VR audio-visual sequence;
- Change in TP after 5-minute exposure to the VR audio-visual sequence;
- Change in HR after 5-minute exposure to the VR audio-visual sequence;
- Change in BP after 5-minute exposure to the VR audio-visual sequence;
- Change in Spielberger State-Trait Anxiety Inventory (STAI) score after 5-minute exposure to the VR audio-visual sequence.

The criterion for the prevailing efficiency for each variable is the presence of statistically significant differences between groups in favour of any of the groups with a directivity, which indicates the effectiveness of the technology. Procedures and methods required for efficacy evaluation are described in Section 4.13. The time and events schedule is shown in Section 4.12.

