9. STATISTICS

9.1 Justification of the sample size

The required sample size is the minimum sufficient number of subjects to obtain clinically and statistically significant outcomes of the clinical trial. Depending on the type of clinical trial and its design, as well as the types of variables used to evaluate the treatment effect, the sample size may vary.

The sample size depends on the following parameters:

- The size of the clinically significant differences (δ);
- Limiting probability of type I error α (usually for the tests of the prevailing efficiency is equal to 0.05 or 5% (two-tail));
- Limiting probability of type II error β (usually equal to 0.2) and, respectively, the power (80 %);
- Estimated on the basis of previous studies of intrasubject variability.

This study is designed to prove the superiority of the use of VR headset A vs. the use of the VR headset B for the main variable — “Change in HFcomponent after 5-minute exposure to the audio and visual VR sequence”.

To estimate the sample size, it is assumed that the following statistical hypotheses are verified for the demonstration of superiority under conditions of the single-group design:

$$H_0: \varepsilon \leq \delta \text{ vs. } H_a: \varepsilon > \delta, \quad (1)$$

where δ — the limit of superiority — the marginal value of the clinically significant differences in which it can be assumed that the investigational device (VR headset A) is superior to the comparable device (VR headset B);

$$\varepsilon = \mu_A - \mu_B \quad (2)$$

true difference between the arithmetic mean of the results obtained using the VR headset A and the VR headset B.

According to Chow et al [18], the sample size can be estimated using the following expression:

$$n = \frac{(z_{\alpha} + z_{\beta})^2 \sigma_m^2}{2(\varepsilon - \delta)^2} \quad (3)$$

where d — the size of clinically important differences as determined by experts; a — limiting probability of type I error (significance level), which in most cases is equal to 0.05 (5%); b — limiting probability of type II error; s_m — coefficient of variation, which is evaluated based on the results of previous studies.

In this study, the size of the clinically important differences d is 0.1 (10%), $a = 0.05$ (two-tailed), $b = 0.05$ (study power of 95 %). It is assumed that the difference e will be 0.25 (25 %), and s_m will be 0.35 (35 %). The results of calculations are given in the table below:

Statistical parameter	Value

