9.2.5 Significance levels

The level of significance is equal to 0.01 for the Shapiro-Wilk test, and equal to 0.05 for other tests.

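### The efficacy criterion in 4.1 and 7.1 names the sequence groups instead of the headsets, and gives each of seven secondary variables the same efficacy label as HF at an unadjusted 0.05

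*Protocol*

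**What the plan says.** Section 4.1 lists one primary variable (HF) and seven secondary ones (rMSSD, LF/HF, SDNN, total power, HR, BP, STAI). It then gives a single decision rule for all of them: "The criterion for the prevailing efficiency for each variable is the presence of statistically significant differences between groups". A direction clause completes the sentence, so that only a difference pointing towards a benefit of the technology counts. Section 7.1 repeats the list, from "Change in HF component after 5-minute exposure to the VR audio-visual sequence" down to "Change in Spielberger State-Trait Anxiety Inventory (STAI) score after 5-minute exposure to the VR audio-visual sequence", and repeats the rule: "statistically significant differences between groups in favour of any of the groups with a directivity, which indicates the effectiveness of the technology".

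Section 9.2.5 sets the level at 0.01 for the Shapiro-Wilk test and "equal to 0.05 for other tests".

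The word *group* is defined in sections 4.2 and 6.1. Group 1 uses headset A and then B. The other is the reverse: "Group 2: the volunteers will first be tested with the VR headset B, and during the next visit – with the VR headset A".

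Section 9.1 states the aim as "This study is designed to prove the superiority of the use of VR headset A vs. the use of the VR headset B", and the same sentence names the HF change as the variable concerned. It defines the effect as the mean under A minus the mean under B. Section 9.2.3 fits a crossover mixed model with sequence, period and headset as fixed factors, and takes the contrast between headsets with B as reference.

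**The concern.** The criterion is stated text, so it can be checked against the rest of the protocol. It fails on two counts.

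**Contrast.** Taken with the protocol's own definition, a difference between groups is a difference between sequences. The question of the trial is the difference between headsets. The model in 9.2.3 contains sequence as a factor of its own, so the analysis output will hold a test that carries the name used in the criterion but does not answer the question.

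**Scope.** The criterion grants the label *prevailing efficiency* to each variable on its own. Nothing in the sentence makes the label for LF/HF or STAI depend on HF. If HF fails and one secondary variable reaches 0.05 in the right direction, the report could say that the protocol's efficacy criterion was met for that variable. The seven secondary variables would then carry the same weight as the variable on which the study was planned.

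**Working it through.** **1. The plan's own figure.** Section 9.1 gives n = (z_α + z_β)² · s_m² / [2(ε − δ)²], with z_α = 1.96, z_β = 1.64, s_m = 0.35, ε = 0.25 and δ = 0.1. Putting these in: (3.60)² × 0.1225 / (2 × 0.0225) = 1.5876 / 0.045 = 35.28, rounded up to 36 (35.37 with unrounded z values). The stated 36 reproduces. It rests on one comparison, HF, at 0.05 two-tailed, which is 0.025 in the favourable direction.

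**2. What a group difference estimates.** Write A and B for the headset means and p1, p2 for the visit effects, with no carry-over.

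- Group 1 over both visits: [(A + p1) + (B + p2)] / 2
- Group 2 over both visits: [(B + p1) + (A + p2)] / 2
- Group 1 minus Group 2: 0, whatever A − B is.

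At Visit 1 alone the group difference is A − B; at Visit 2 alone it is B − A. Pooled over visits the headset effect cancels. The within-subject contrast of 9.2.3 recovers it; the group comparison does not.

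**3. Error over the eight variables.** The criterion has a direction clause, so under no effect each variable meets it with probability 0.05 / 2 = 0.025.

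- HF alone: 2.5% favourable (5% two-sided).
- At least one of eight, independent tests: 1 − 0.975⁸ = 18.3%.
- Under any dependence, by simple addition: no more than 8 × 0.025 = 20%.

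The protocol gives no correlations. With an assumed common correlation between the test statistics, each oriented so that positive is favourable, simulation with one million draws gives the middle column. Subtracting the 2.5% for HF leaves the chance that a secondary variable meets the criterion while HF does not.

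| Assumed correlation | Any of eight favourable | Of which HF not met |
|---|---|---|
| 0 | 18.3% | 15.8% |
| 0.3 | 15.2% | 12.7% |
| 0.5 | 12.5% | 10.0% |
| 0.7 | 9.5% | 7.0% |
| 0.9 | 5.9% | 3.4% |

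If BP is analysed as systolic and diastolic (an assumption), there are nine tests, and independence gives 1 − 0.975⁹ = 20.4%.

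**4. Margin.** The null hypothesis in 9.1 is that the difference is at most δ = 0.1. The criterion in 4.1 and 7.1 asks only for a significant difference and does not mention the margin. The two do not describe the same test.

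**The case against.** The protocol does separate one primary variable from seven secondary ones, and 9.1 ties the superiority aim and the sample size to HF alone. The criterion speaks of efficacy for each variable and nowhere says that one positive secondary variable makes the trial a success. A reader might infer an any-of-eight success rule; the documents do not state one, and the primary claim keeps its nominal error. That stands. The figures above apply only if a secondary result is presented as efficacy, which the criterion permits.

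A reader might also quote 1 − 0.95⁸ = 33.7%. That counts results against the technology, which the direction clause rules out. Even 18.3% assumes independence, which is not realistic here: HF is the denominator of LF/HF, and section 2 links the fall in total power under stress to the fall in HF.

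A third inference would be that the wrong contrast will be analysed, or that a significant sequence effect will be called efficacy. Section 9.2.3 specifies the headset contrast, and the direction clause makes sense only for headset against headset. So the contrast problem is contradictory wording in 4.1 and 7.1, not a faulty model.

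Last, a hierarchy for secondary variables may sit in a statistical analysis plan that is not shown. Its absence from the protocol is no fault in itself. But the protocol does fix a per-variable efficacy rule, and a later hierarchy would have to override that text.

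**Conclusion.** The point holds as a correction to one sentence that appears twice. The criterion names groups where 9.1 and 9.2.3 require headsets. It also gives seven secondary variables the same efficacy label as HF at an unadjusted 0.05, against an aim that concerns HF alone.

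The HF test is sound on this point. The exposure lies in secondary claims: about 18% if the eight tests were independent, about 12.5% and 9.5% at assumed common correlations of 0.5 and 0.7, against 2.5% for a favourable result on HF alone. These figures assume no true effect on any variable, eight tests and equal correlations; planned subgroup analyses are not counted. The contradiction over groups and the mismatch with the margin need no assumption, since both follow from the text.

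**What to change.** In sections 4.1 and 7.1, replace the criterion with text to this effect:

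- The comparison is between headsets (A versus B, the contrast of 9.2.3).
- The efficacy conclusion rests on that contrast for HF, in favour of A.
- The other seven variables are supportive. Alternatively, they are tested only after HF has succeeded, in a stated fixed order or with Holm at 0.05 (first step 0.05 / 7 = 0.0071).

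The choice between supportive and formally tested is the sponsor's. STAI serves the separate secondary objective in section 3, so it may merit an early place in a fixed order.

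In the same amendment, state whether success on HF means a difference above zero or above the 0.1 margin of 9.1, and make the criterion, the hypotheses and the sample size agree.

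The cost is one sentence in two places, plus the reconciliation with 9.1. The change of criterion alters no procedure, data collection or planned number of volunteers. The downside is that an isolated positive secondary result can no longer be called efficacy. Because the text defines success, it should be settled before unblinding.

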Efficacy evaluation	
Primary variable:
 
 • Change in HF component after 5-minute exposure to the VR audio-visual sequence; 
Secondary variables:
 
 • rMSSD variable after 5-minute exposure to the VR audio-visual sequence; • LF/HF ratio after 5-minute exposure to the VR audio-visual sequence; • SDNN variable after 5-minute exposure to the VR audio-visual sequence; • Total power (TP) variable after 5-minute exposure to the VR audio-visual sequence; • HR variable after 5-minute exposure to the VR audio-visual sequence; • BP variable after 5-minute exposure to the VR audio-visual sequence; • Spielberger State-Trait Anxiety Inventory (STAI) variable after 5-minute exposure to the VR audio-visual sequence.

Safety and tolerability evaluation	
For the purposes of safety evaluation, security measures will be taken and the following data will be evaluated:
 
 • the number of AE/ADE occurring during the participation in the study; • the results of measurement of vital signs; • the overall tolerability evaluation of the VR technology provided by the investigator.
Examination methods	
The following examination methods will be used during the study:
 
 • Collection of medical history; • Anthropometric examination (weight, height); • Measuring BP, HR, RR, and body t°; • Spielberger State-Trait Anxiety Inventory (STAI); • Electrocardiography.

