2.1. Name and description of the VR technology

Studied VR technology

The **Pure Purr** technology consists of a virtual reality headset with pre-installed software. The virtual reality headset reproduces a dynamic video content that is visually perceived with the help of the high-resolution screen. Also, the headset is able to play audio and transmit it via the headphones. During the Pure Purr study, the volunteer puts on the BoboVR X1 headset, which creates the illusion of a gazebo located by the ocean. The visual sequence also includes a horizon created by the surface of the ocean and blue sky. The dynamics is achieved with the help of the ocean waves moving towards the observer. Curtains enclosing the gazebo from two opposite sides are also moving as if fluttering with fresh wind, and in front of the eyes of the observer a cat is walking in time with the calm breath of a person. The audio support was created on the basis of a slow musical composition and modified by adding a binaural effect, and a background cat purring that was slowed down and supplemented with a binaural effect.

The total length of the audio-video sequence is 6 minutes 11 seconds, of which 1 minute 11 seconds is the Pure Purr promotional video, and the duration of the investigational audio-visual sequence itself is 5 minutes.

Sham VR technology

The sham technology includes an identical BoboVR X1 virtual reality headset with pre-installed software. The audio-visual sequence is similar to the one in the investigational version of the software. The key difference is that the audio sequence has not been modified with the binaural effect and has not been synchronized with the tact of respiratory movements and the frequency of heart rate.

The total length of the audio-video sequence is 6 minutes 11 seconds, of which 1 minute 11 seconds is the Pure Purr promotional video, and the duration of the investigational audio-visual sequence itself is 5 minutes.

Figure 1. Still frame of the visual sequence seen by the volunteers during the study of the effect of the VR technology (sham).

Figure 2. Still frame of the visual sequence seen by the volunteers during the study of the effect of the VR technology (studied technology).

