4.12. Time and events schedule

The frequency of examination in volunteers and registration of the data obtained will be carried out in accordance with the schedule shown in Table 4.

Table 3. Visit matrix (time and events schedule)

Study procedures		
Visits ¹	Visit 1	Visit 2
Study days	Day 1	Day 2 (+7)
Basic data		

Study procedures		
Visits ¹	Visit 1	Visit 2
Study days	Day 1	Day 2 (+7)
Obtaining informed consent	X	
Evaluation of volunteer's compliance with the inclusion/non-inclusion criteria	X	
Randomization	X	
Evaluation of availability of exclusion criteria		X
Registration of demographic data	X	
Collection of medical history	X	
Physical examination	X	X
Measuring BP, HR, RR, and body t°	X	X
Registration of concomitant treatment and comorbidities	X	
Investigation of the VR technology		
Stress modulation and EGC recording before/during/after VR exposure	X	X
Evaluation of volunteers based on the Spielberger State-Trait Anxiety Inventory (STAI)	X	X
Safety and tolerability evaluation		
Registration of AR/ADE	X	X
Tolerability evaluation	X	X

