4.14. Study data collection procedure

The study will be collected according to the following plan:

Visit 1.

The visit takes place at the SS and is considered to be Day 1 of the study.

Having received the informed consent for participation in the study, the investigator evaluates the compliance of the volunteer with the inclusion criteria and verifies that he/she has no non-inclusion criteria.

During the visit, the investigator:

- Obtains the Informed Consent Form from the volunteers;
- Checks the inclusion/non-inclusion criteria, evaluates the volunteers with the help the Spielberger STAI. In case a volunteer has all the inclusion criteria and no signs that meet the non-inclusion criteria, the investigator performs further data collection and randomization;
 - Anthropometric data (weight, height and body mass index);
 - Evaluates vital signs (BP, HR, RR, and body t°);
 - Physical examination;
 - Collects demographic data (date of birth, gender);
 - Collects clinical data on concomitant diseases, therapy and records them;
 - Investigates the technology of virtual reality (Stages 1, 2, 3, and 4);
 - Evaluates the volunteers' complaints in terms of the development of adverse events/adverse device effect (AE/ADE);
 - Evaluates tolerability;
 - The clinician records all indicators collected at Visit 1 and transfers them to the CRF.

Visit 2.

The visit takes place at the SS.

During the visit, the Investigator:

- Checks the inclusion criteria. In case a volunteer has no signs that meet the exclusion criteria, the Investigator performs further data collection;
 - Evaluates vital signs (BP, HR, RR, and body t°);
 - Evaluated physical signs;
 - Investigates the technology of virtual reality (Stages 1, 2, 3, and 4);
 - Evaluates volunteers based on the Spielberger State-Trait Anxiety Inventory (STAI);
 - The investigator records all indicators collected at Visit 2 and transfers them to the CRF;
 - Evaluates the volunteers' complaints in terms of the development of adverse events/adverse device effect (AE/ADE);
 - Evaluates tolerability;
 - Informs volunteers on study completion.

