5. INCLUSION AND EXCLUSION OF THE SUBJECTS

It is planned to enrol approximately 160 healthy volunteers to the study for further randomization of 100 volunteers.

For the purposes of randomization the volunteers should meet the inclusion criteria and have no non-inclusion criteria, be familiar with the terms of participation in the study, and sign the Informed Consent Form for participation in the study.

5.1. Inclusion criteria for the study subjects:

The study will enrol healthy volunteers meeting all the following inclusion criteria:

1. Females and males 20-60 years old;
2. Volunteers have no history of cardiovascular diseases;
3. Volunteers have no essential abnormalities of the ECG;
4. Normal or moderate level of situational anxiety based on the Spielberger State-Trait Anxiety Inventory (STAI);
5. Signed Informed Consent Form for participation in the study.

5.2. Non-inclusion criteria for the study subjects:

The study will not enrol volunteers meeting one or more non-inclusion criteria:

1. Intolerance to the VR technology;
2. HR above 110 bpm or below 50 bpm;
3. RR above 23 breaths per minute;
4. Abuse of alcohol, psychotropic substances and narcotic agents;
5. Smoking more than 100 cigarettes a week;
6. Administration of medicinal products for the treatment of cardiovascular and nervous system diseases 3 days prior to participation in the study;
7. Drinking tonics and energy drinks for at least 2 hours prior to participation in the study;
8. Severe or acute forms of respiratory, urogenital, gastrointestinal, haematological, metabolic, endocrine, or neurological diseases;
9. Mental disorders, which, in the opinion of the investigator, may distort the results of the study;
10. Participation in any clinical study over the last 3 months prior to enrolment to the study;
11. Parkinson's disease, Parkinson's symptoms, tremor, restless leg syndrome, and other motility disorders;
12. Pregnancy;
13. Any disease of the thyroid gland.

5.3. Exclusion criteria for the subjects:

The study will not enrol volunteers meeting one or more exclusion criteria:

1. Emergence of any medical condition, an adverse event or circumstances when, in the opinion of the investigator, it is not in the best interests of the volunteer to proceed with the participation;
2. Failure to comply with the requirements of the protocol;
3. Onset of one of the non-inclusion criteria.

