9.2.4 Safety and tolerability analysis

Provide parameters of descriptive statistics used to assess the safety and tolerability of each individual headset.

Since the safety of the product will be evaluated based on the development (or lack thereof) of negative (undesired) adverse events and reactions, the parameters of descriptive statistics (frequency and rate as a percentage) should be provided. Evaluate serious AR/ADE and non-serious AR/ADE both together and separately.

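### Section 4.1 times the Table 1 tolerability score once, after both headsets, while 4.12 and 4.14 schedule tolerability at each visit and 9.2.4 wants it by headset (minor)

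*Protocol*

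**What the plan says.** Section 4.1 (Tolerability evaluation) first bases tolerability on vital signs and on the assessment of adverse reactions and device effects (AR/ADE). It then introduces Table 1, a 5-point investigator rating: "Upon completion of the study (upon completion of Visit 2), the Investigator should provide an assessment of the tolerability of the studied VR technology". One rating is due per volunteer. Table 1 is the only tolerability scale in the protocol.

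Other parts of the protocol treat tolerability as follows:

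- **Section 4.12, Table 3** has a row for "tolerability evaluation" marked at both Visit 1 and Visit 2, separate from AR/ADE registration and from vital signs.
- **Section 4.14** lists "Evaluates tolerability" under both visits, again as its own item.
- **Section 9.2.4** instructs: "Provide parameters of descriptive statistics used to assess the safety and tolerability of each individual headset".
- **The synopsis** names three safety items, one of which is "the overall tolerability evaluation of the VR technology provided by the investigator".

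**The concern.** In this cross-over each volunteer uses one headset at Visit 1 and the other at Visit 2. A single rating given after Visit 2 follows exposure to both and carries no headset label, so as it stands it cannot feed a summary by headset. The schedule and the visit procedures point to two evaluations, and the analysis section needs the result for A and for B.

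The timing also matters for withdrawals. The event that triggers the 4.1 rating is completion of Visit 2. Score 2 is given for a significant reaction where "it requires discontinuation of the use of the VR technology, but does not require additional medical care", and score 1 for one that needs both stopping and care. A volunteer with such a reaction at Visit 1 may be withdrawn under exclusion criterion 1 in section 5.3, or under criterion 3 by way of non-inclusion criterion 1 ("Intolerance to the VR technology"). Such a volunteer never reaches the one time at which 4.1 calls for a rating, and section 5.3 does not allow replacement. The rule therefore tends to omit the two worst categories when they arise at Visit 1.

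At stake is whether one of the three safety items in the synopsis is collected in the form that the analysis section asks for.

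**Working it through.** The protocol states no figure here, so the check is a comparison of the sections followed by a count.

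**Step 1. Ratings due under each section.**

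| Source | Completer | Withdrawn after Visit 1 | Labelled by headset? |
|---|---|---|---|
| 4.1 (names Table 1) | 1 | 0 | No |
| 4.12 and 4.14 (name no scale) | 2 evaluations | 1 evaluation | Yes, through the visit |
| 9.2.4 (requirement) | 2, one per headset | 1, for the headset used | Yes |

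With the planned 100 randomised volunteers (section 4.3, Table 2) and two exposures each:

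- planned exposures: 2 × 100 = 200
- ratings under 4.1: at most 1 × 100 = 100
- ratings if Table 1 is scored at each visit: up to 2 × 100 = 200

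**Step 2. Readings that might reconcile the sections.**

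- *Visit evaluations plus one closing rating.* Sections 4.12 and 4.14 name no scale. Unless Table 1 is also meant at the visits, it is still scored once.
- *The visit item is only the review of vital signs and AR/ADE.* Both sections list those separately. Even on this reading, Table 1 is scored once.
- *The 4.1 rating concerns Pure Purr alone.* Section 2.1 uses "Studied VR technology" as the heading for Pure Purr, as against the sham. The sham headset would then have no rating, and 9.2.4 would not be met for it.

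**Step 3. What other records can supply.** Section 8 requires, for every AR/ADE, the dates and times of start and end, nature, severity, likelihood of a connection with the technology and measures taken. Its list of actions includes stopping the technology, treatment and hospitalisation. The Headset Use Form (section 4.8) records date, time, headset A or B and volunteer. Against the Table 1 categories:

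- **5** (no related adverse reaction): follows from the absence of a related record for that session.
- **2 and 1** (stopping needed, without or with medical care): follow largely from the actions recorded, including for a volunteer withdrawn after Visit 1.
- **4 versus 3** (a minor effect without or with discomfort): not settled by these records. Severity Table 5 grades mainly by the intervention needed and does not grade discomfort. Nature and severity inform the choice but do not replace the investigator's rating.

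**The case against.** The strongest reply has three parts.

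*Section 9.2.4 can be met without Table 1.* It does not mention the scale. It asks for descriptive statistics and then specifies AR/ADE frequency and rate, while 4.1 itself bases tolerability on vital signs and AR/ADE, which are collected at each visit. This stands in part: headset-level safety and most of headset-level tolerability can be reported. It does not explain why the investigator's rating, the only scale given for tolerability, is timed so that it does not contribute by headset.

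*Sites may use Table 1 at each visit anyway.* The row in Table 3 has the same title as Table 1, 4.1 does not forbid a rating at each visit, and the synopsis speaks of an overall evaluation that could be an extra closing score. This is plausible, and the case report form, which would settle it, is not shown. But the only sentence that names the scale also fixes its time at the end of Visit 2. A site could equally follow that sentence literally.

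*An overall rating is legitimate.* Both headsets are the same model with similar content, and the foreseen effects are those of virtual reality in general. That supports keeping an overall score, but not having it as the only one when 9.2.4 asks for each headset.

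A reader might infer that headset-specific tolerability is irretrievably lost, or that a volunteer stopped at Visit 1 leaves no tolerability information. The protocol does not support either inference: the dated AR/ADE records, the actions taken and the Headset Use Form remain attributable to a session and a headset.

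**Conclusion.** The instruction in 4.1 conflicts with the visit schedule and procedures, and does not deliver the rating in the form that 9.2.4 needs. Followed literally, it records no rating by headset and requires none for a volunteer withdrawn after Visit 1.

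The consequence is small. Mainly the investigator's own judgement for each headset is lost, notably the distinction between 4 and 3. Volunteers with no related reaction at either visit lose nothing. The protocol gives no reaction rate, so the number of volunteers affected cannot be estimated. Tolerability is described and not tested, and no efficacy result depends on it.

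This rests on two assumptions: that 4.1 is applied as written, and that AR/ADE and headset use are recorded as sections 8 and 4.8 require. If the case report form already has a Table 1 field at each visit, only the wording of 4.1 is at fault. Severity: minor.

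**What to change.** Reword the timing sentence in 4.1: at the end of each visit, and at withdrawal if a session is stopped, the investigator gives the Table 1 score for the headset (A or B) used at that visit. An additional overall score after Visit 2 may be kept, so the synopsis can stay as it is. Sections 4.12, 4.14 and 9.2.4 and severity Table 5 need no change.

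The cost is one sentence in the protocol and one Table 1 field per visit in the case report form. No procedure is added, because a tolerability evaluation is already scheduled at both visits. The change must precede data collection: an investigator's rating by headset that was not made at the time can later only be approximated from the adverse-event records.
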